3. Any serious disease, or chronic condition, that could interfere with the study compliance
4. Unwilling to have a synthetic sling
5. Inability to give informed consent
6. Pregnancy or planning pregnancy in the first postoperative year
7. Untreated urinary tract infection (may be included after resolution)
8. Poorly-controlled diabetes mellitus (HgbA1c > 9 within 3 months of surgery date)
9. Prior pelvic radiation
10. Incarcerated
11. Neurogenic bladder/ pre-operative self-catheterization
12. Elevated post-void residual (>150 ml) that does not resolve with prolapse reduction testing (pessary, prolapse reduced uroflow or micturition study)
13. Prior augmented (synthetic mesh, autologous graft, xenograft, allograft) prolapse repair
14. Planned concomitant bowel related surgery including sphincteroplasty and perineal rectal prolapse surgery, rectovaginal fistula repair, hemorrhoidectomy.

STUDY POPULATION, RECRUITMENT AND SCREENING

Study population participants will consist of women having native tissue vaginal repair in any vaginal compartment. Participants must have vaginal bulge symptoms defined by positive responses to a validated instrument, the Pelvic Floor Distress Inventory²³ and Stage II or greater POP in any vaginal compartment as determined by the Pelvic Organ Prolapse Quantification (POPQ) system²⁴, a validated tool designed to assess the degree of vaginal prolapse. Participants must have objective evidence of stress incontinence on physical examination, with or without prolapse reduction, or on urodynamic testing. Women will be grouped according to whether they have SYMPTOMATIC or OCCULT SUI for randomization purposes.

Study subjects will be recruited from patients who present to the urogynecology clinical sites at Wake Forest Baptist Health, the Women's Health Institute at the Cleveland Clinic, Northwestern, MedStar Washington Hospital Center, Women's and Infants' Hospital of Rhode Island, Atrium Health, and Groote Schuur Hospital at the University of Cape Town, and the private practice clinic of [name]. Wake Forest Baptist Health will serve as the central Data Coordinating Center. Institutional review board (IRB) approval will be obtained at each participating site.

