Potential subjects will be identified by members of the sections of Urogynecology and Reconstructive Pelvic Surgery and Benign Gynecology at the respective institutions. Eligible patients who agree to participate will be provided written informed consent administered by the collaborators listed on each Institutional IRB document.

PRE-INTERVENTION ASSESSMENTS:

All women presenting to the participating clinical centers with signs and symptoms of prolapse and objective stress incontinence (symptomatic or occult) will be screened for their eligibility. If eligible and consenting, the following baseline data will be collected on paper forms that will then be transcribed into a secure RedCap database:

1. Demographic data including age, race, BMI, insurance status
2. Health-related quality of life (SF-12), and measurement of Charlson Comorbidity Index
3. Smoking status (Yes or No)
4. POP-Q data
5. Presence of vaginal atrophy (Yes or No)
6. Menopausal status, including current exposure to topical vaginal estrogen, parity, and urogynecologic surgeries
7. Current exposure to anticholinergic medication (Yes or No)
8. Objective assessment of stress incontinence: Clinical or urodynamic assessment is permitted.
 - a. **Clinical cough stress test:** Participants that have no prior objective SUI will be instructed to present with a full bladder . If empty, the bladder can be retrograde filled with 300 ml. In the lithotomy position, subjects will be asked to **cough and strain (Valsalva) while the urethral meatus is observed and the POP is reduced.** If no leakage is demonstrated, the reduction cough stress test will be repeated in the standing position. **Women will be categorized as having symptomatic vs occult SUI for sub-analysis and block randomization.**
 - b. **Urodynamic testing:** Participants may undergo standard urodynamic testing with prolapse reduction. A cough stress test at bladder capacity will be performed. If no leakage is demonstrated at capacity with the catheters in place, the catheters will be removed and the cough stress test repeated. Valsalva leak point pressures will be recorded.
9. Assessment of post-void residual volume (collected via bladder scan or CIC)
10. A series of instruments will be used to measure symptom bother: the Pelvic Floor Distress Inventory short form-20,²³ Pelvic Organ Prolapse/Urinary Incontinence Sexual Functioning Questionnaire Short Form (PISQ-IR)²⁵ and PFIQ-7.

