NOTE: Standard of care assessments (POP-Q, UDS, PVRs) are valid to use for the study if they were performed within 6 months of the subject signing consent. Also, if any standard of care questionnaires (matching the study questionnaires) were administered within 6 months before signing consent, they may also be used

in the place of baseline questionnaires and not repeated. Dates of assessments just need to be clear if they were not performed the same day as baseline. Also, make sure all assessments required for the study have been performed per baseline visit requirements.

RANDOMIZATION AND MASKING:

A computer-generated random allocation using a randomly permuted block design (10 subjects per block) will be stratified by clinical site and presence of symptomatic versus occult SUI. Randomization will be assigned in the operating room to minimize surgeon and participant bias. While it is impossible for surgeons to be masked to the randomization, participants will be masked during the one-year follow-up period. Dictated operative notes will list the type of sling under procedures as “per study protocol” and then describe the type of sling used within the body of the operative note. Precautions will be taken to minimize unmasking the study groups: Since RP slings require two suprapubic stab incisions, identical sham incision will also be performed in the SIS group. Surgical wound dressings will be identical for all participants. Finally, all participants, regardless of randomization, will have postoperative indwelling urethral catheters until voiding trials are performed.

STUDY INTERVENTION:

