The primary intervention is concomitant placement of any full-length macroporous, monofilament polypropylene bottom-up Retropubic Sling (manufactured by Boston Scientific; Ethicon; Caldera; or Neomed) VERSUS Altis™ single-incision sling (Coloplast, Minneapolis, MN) during completion of native tissue vaginal repair, including colpocleisis. If an anterior or apical procedure is planned, the sling must be tensioned following completion of these steps. Prolapse procedures will be recorded but not controlled by study protocol. Participating surgeons are all extensively experienced in RP sling passage and are required to have performed at least 5 SIS procedures prior to enrolling participants in this trial. In order to minimize the risk of altering the urethrovesical angle and the likelihood of postoperative stress urinary incontinence, any anterior repair will be conducted using an incision proximal to the bladder neck level and separate from sling incisions. Allowable techniques for prolapse repair include anterior and posterior colporrhaphy (plication of fibromuscular vaginal tissue), vaginal paravaginal repair, sacrospinous ligament suspension (either of uterus or vaginal apex), uterosacral ligament suspension (either of uterus or vaginal apex, through vaginal or laparoscopic approach) levator plication or colpocleisis. Any use of allograft, xenograft, or synthetic graft material for POP repair will not be permitted.

Standardized technique of RP sling placement

Retropubic procedures will all be performed using the vaginal or “bottom-up” approach as described by the manufacturers (Ethicon; Boston Scientific; Caldera; Neomed). Subjects will be placed in Trendelenburg position, the legs lowered to lithotomy position, and the bladder completely drained. A 1.5 cm incision will be made at the mid-urethra through a separate vaginal incision with lateral dissection with Metzembbaum scissors. After placement of both trocars, cystoscopy with a 70-degree scope will be performed to assess for bladder and urethral injury. Surgeons will set the tension of the TVT slings so that a spacer can be placed between the sling and the urethra. Sling tensioning will be performed after anterior and apical prolapse is corrected. Dermabond or steri strips will be applied to the suprapubic exit incisions.

Standardized technique of SIS placement

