Site staff must not make any changes or deviate from this protocol, except to protect the life and physical well-being of a subject in an emergency. Site staff shall notify the PI and the reviewing IRB of any deviation from the investigational plan to protect the life or physical well-being of a subject in an emergency, and those deviations which affect the scientific integrity of the clinical investigation. Such notice shall be given as soon as possible, but no later than 5 working days after the emergency occurred. Local IRB/regulatory requirements will prevail if sooner than 5 working days. All deviations from the investigational plan, with the reason for the deviation and the date of occurrence, must be documented and reported to the Data Coordinating Center. Study sites may also be required to report deviations to their IRB per local guidelines and government regulations.

Data Safety Monitoring Board

A data safety monitoring board (DSMB) will be established that is made up of two independent physicians with no connection to the conduct of this clinical trial who have no relevant conflicts of interests. The PI will review the DINDO grading of any sling related post adverse events within 48 hours of reporting and will immediately report these events to the DSMB. The DSMB will receive a progress report of study recruitment, enrollment, and retention every 6 months and make a determination regarding appropriate continuation of the study.

REPORTING ADVERSE EVENTS:

Adverse events will be recorded and reported according to criteria and timeline below. Sites will also follow local regulatory standards for AE reporting.

All study-related AEs must be recorded on the AE CRF supplied by the coordinating site, entered into the site AE log, then entered into REDCap. Each AE will be sequentially numbered according to patient. For example, patient 003's first AE would be 003.01. Each site investigator will determine the relationship of the AE to the operative procedures, the relationship of the AE to the device, along with the severity of each reportable AEs. All complications will be evaluated by the sub-sites with PI ([name]) being the deciding factor for the DINDO score (See Table Below). The sub-sites will also determine if the complications are more likely to be related to the overall surgery, sling surgery or both. Complications that are deemed not related to the surgery will be excluded (For example, a MI at >3mo postop.)

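### The Protocol discloses a single fixed block size of 10 within site-by-SUI strata, so anyone who tracks a whole stratum could know some upcoming allocations with certainty

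*Protocol*

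**What the plan says.** Under Randomization and Masking, the Protocol describes a "randomly permuted block design (10 subjects per block) will be stratified by clinical site and presence of symptomatic versus occult SUI". It names no other block size and does not restrict who may know this one. The same section states that "it is impossible for surgeons to be masked to the randomization", and offers one safeguard against anticipation: "Randomization will be assigned in the operating room to minimize surgeon and participant bias".

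The stratum is settled well before surgery. Under Pre-Intervention Assessments, "Women will be categorized as having symptomatic vs occult SUI for sub-analysis and block randomization". Eight recruiting locations are listed under Study Population, Recruitment and Screening, so there are up to 16 strata.

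Sites work from this document (Protocol Deviations: "Site staff must not make any changes or deviate from this protocol"), so the block length can be read there. Under Study Intervention, "Prolapse procedures will be recorded but not controlled by study protocol", which leaves the surgeon discretion over the accompanying repair.

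**The concern.** Permuted blocks conceal the next allocation only while both arms still have places left in the block. With a published fixed length, an observer who counts allocations knows when one arm is used up, and from then on the rest of the block is no longer random to that observer. All the ingredients are present here: the length is printed, the count is kept within site, the stratum of the next woman is known in advance, and surgeons see which sling they place.

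What is at stake is selection before allocation. Someone who can deduce the next assignment could change the order of cases on a list, move a woman's date, or plan the prolapse repair with the sling in mind. Any of these could make the two arms differ in case mix or accompanying surgery. Analysing the women as treated or as randomised does not repair that. In a trial judged against a 12-point non-inferiority margin, such a difference could work in either direction.

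**Working it through.** **Inputs.** From the Protocol: block size 10; strata are site by symptomatic or occult SUI; 8 sites listed; enrolment goal 280. Assumed: five of each sling per block (1:1 is implied by the equal groups in the Power Calculation, not stated); strata of equal size, 280 / 16 = 17.5 women; an observer who knows every earlier allocation in the stratum. The Protocol gives no predictability figure to reproduce.

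**One complete block.** There are C(10,5) = 252 equally likely blocks. Allocation k is certain if the first k − 1 already contain all five of one sling, so

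P(k certain) = 2 × C(k − 1, 5) / 252.

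| Position | Calculation | Probability certain |
|---|---|---|
| 6th | 2 × 1 / 252 | 0.8% |
| 7th | 2 × 6 / 252 | 4.8% |
| 8th | 2 × 21 / 252 | 16.7% |
| 9th | 2 × 56 / 252 | 44.4% |
| 10th | 2 × 126 / 252 | 100% |

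The expected number is 2 × (1 + 6 + 21 + 56 + 126) / 252 = 420 / 252 = 1.67 of 10, or **16.7%**. Always guessing the arm with more places left is right 65.3% of the time.

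**A stratum of 17.** One full block contributes 1.667. The first seven places of the second block contribute 0.008 + 0.048 = 0.056. The share is (1.667 + 0.056) / 17 = 1.722 / 17 = **10.1%**. By simulation the best guess is right 62.5% of the time. Applied to 280 women, 10.1% is about 28.

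**Unequal strata.** Simulating 280 women over 8 sites, with equal or unequal site weights and a symptomatic share of 50–80% (both assumed), gives 35 to 37 certain allocations, about 13%.

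**What the observer knows.** Suppose cases in a stratum of 17 are split evenly at random between surgeons, and each knows the block boundaries but only her own allocations. The certain share falls from 10.1% (one surgeon) to about 0.3% (two) and 0.04% (three). The Protocol does not give the number of surgeons per site.

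**Alternatives, strata of 17.** The observer knows all past allocations and, for varying sizes, also the set of possible sizes.

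| Scheme | Certain | Best guess right |
|---|---|---|
| Fixed 10 | 10.1% | 62.5% |
| Random 8, 10, 12 | about 1.7–1.8% | about 63% |
| Random 4, 6, 8 | about 2.4% | about 66% |

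If the set of sizes is not known, no allocation can be certain. Short varying blocks also remove most of the certainty, but they make ordinary guessing easier.

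**The case against.** The case for leaving the text alone has several parts.

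- **The observer is assumed.** The masking sentence covers surgeons and the cases they operate on. Nothing says that each surgeon sees all allocations at her site. Recruitment draws on members of two sections, and the Authorship section mentions recruiting co-investigators, so several operators per site are likely. This stands: a reader might infer that about 28 women will have predictable allocations, but that is a full-information figure. It does not clear the design, because colleagues may share counts and coordinators may see all cases.
- **Late assignment.** Block position follows the order of surgery, not of consent, so steering whom to approach is difficult. This stands in part. Assignment in the operating room prevents an early look at the allocation, but it does not prevent counting. Case order and planning close to surgery remain open.
- **Retreatment.** A reader might infer that predictability biases the primary outcome through retreatment decisions by unmasked surgeons. The Protocol does not support that. Those decisions follow surgery, when the sling is known under any block scheme, and the text does not say that the same surgeon makes them. The symptom component is reported by masked participants.
- **Ten is already long.** In complete blocks, a fixed size of 4 gives 33.3% certain and a fixed size of 6 gives 25%. That is true, and it is why the replacement should not use short blocks.
- **Guessing does not improve.** The best-guess rate stays near 63%, so the gain lies in removing certainty only. This is correct.

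**Conclusion.** The point holds as a modest, avoidable weakness in allocation concealment. With a disclosed fixed block of 10 within site-by-SUI strata, a person who tracks a whole stratum could know about 10% of allocations in advance (16.7% in complete blocks, about 13% if strata vary in size). These figures assume 1:1 blocks, 16 strata and full knowledge of past allocations. They are upper bounds where surgeons see only their own cases, and with two or more such surgeons the share is below 1%.

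The exposure is limited to case order, scheduling and pre-operative planning by predicted arm. The Protocol gives no evidence that anyone has acted on a prediction, and the sample size is unaffected. A statistical analysis plan could not cure this, because the length is already printed in the document that sites hold.

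**What to change.** In Randomization and Masking, replace the parenthesis that gives the block length with: *randomly varying block sizes not disclosed to sites*. Keep the sizes of similar length, for example 8, 10 and 12, and hold them in a separate document known only to the statistician at the data coordinating centre. That restriction matters because the coordinating centre is also a recruiting site. Apply the new scheme to the unused part of the list.

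The cost is small but not nil: the unused list must be regenerated, and Study Monitoring requires IRB or equivalent approval of a revised protocol at each site before implementation. Staff who have read the current text keep their knowledge for any block left open under the old list. The change helps only women not yet randomised. Parts of the Power Calculation are written in the past tense, so enrolment may be over, though the Protocol does not say so. In that case the text cannot be repaired, and the fixed, disclosed block size should be reported as a limitation.

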To conduct a multi-center, prospective, randomized, single-blind trial of retropubic (RP) versus single-incision sling (SIS) in women with \geq Stage II pelvic organ prolapse and objectively confirmed stress urinary incontinence who are undergoing native tissue vaginal repair.

The **primary outcome** will be **abnormal lower urinary tract function**, a composite outcome defined as the presence of any the following at 1 year post-surgery: subjective stress incontinence symptoms or retreatment for persistent / de novo stress urinary incontinence or retreatment for urinary retention. This study is a non-inferiority study design.

Hypothesis 2: SIS is associated with fewer intra-and post-operative complications up to 1 year following surgery due to fewer sling related complications including urinary tract injury; bleeding; de novo or worsening urge incontinence symptoms; urinary tract infection, mesh exposure, need for prolonged catheter drainage and reoperations than RP slings.

Specific Aim 2:

To compare intra- and post-operative sling related complications, de novo or worsening urge incontinence symptoms and need for prolonged bladder drainage up to 1 year post-operatively in women randomized to RP versus SIS sling at the time of native tissue vaginal repair.

SUBJECT SELECTION

Inclusion Criteria

1. At least 21 years of age
2. Women being considered for a native tissue vaginal repair in any vaginal compartment or colpocleisis
3. POP \geq stage II of any vaginal compartment, according to the pelvic organ prolapse quantification (POP-Q) system [31]
4. Vaginal bulge symptoms as indicated by an affirmative response to question 3 of the PFDI-SF20 with some degree of bother (answer must be somewhat, moderately, or quite a bit): Do you usually have a bulge or something falling out that you can see or feel in the vaginal area?
5. Positive standardized cough stress test on clinical examination, or on urodynamic testing
6. Understanding and acceptance of the need to return for all scheduled follow-up visits and willing to complete study questionnaires
7. Able to give informed consent

Exclusion Criteria

1. Prior surgery for stress urinary incontinence including mid-urethral sling; Burch/MMK; fascial pubovaginal sling (autologous, xenograft or allograft; urethral bulking injection)
2. Status post reconstructive pelvic surgery with transvaginal mesh kits or sacrocolpopexy with synthetic mesh for prolapse

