All surgeons will watch a standardized video regarding SIS sling placement prior to study launch. A 1.5 cm incision will be made at the level of the mid-urethra. The sling/needle assembly is advanced behind the ischiopubic rami in a transobturator trajectory toward the obturator space bilaterally. The needle is then removed by simply sliding the fixating tip back out. The other side is then completed in an identical fashion. The sling will be tensioned so that it will lie in direct apposition to the urethra but will still permit passage of an instrument between the mesh and the urethra. The adjustment thread is then cut short and the vaginal incision is closed with an absorbable suture.

Following SIS placement, **2 small superficial skin incisions will be made in the same location as the exit sites of a RP sling.** Dermabond or steri strips will be applied.

Any intra-operative adverse events will be recorded on data collection forms.

Post-operative care and procedures for voiding trials will not be standardized. Day of discharge and method of voiding (spontaneous, self-catheterization, suprapubic catheter, or indwelling foley) will be recorded.

POST-INTERVENTION ASSESSMENTS:

The primary study endpoints will be assessed at 6 weeks and 12 months after the index surgery via a clinic visit and health-related quality of life interview/completion of questionnaires. Individual site study coordinators will collect follow-up healthcare utilization data and update the medical history at 6 and 12 months. Study coordinators will complete a telephone interview at 6 months to assess for any Adverse Events.

Clinical outcomes

This trial has a composite **primary** dichotomous outcome of **abnormal lower urinary tract function** at 12 months post-operatively (YES or NO) that is defined as ANY of the following:

1. Subjectively bothersome stress incontinence symptoms at 12 months post-operatively, as measured by a positive response of > 1 to Question 17 on PFDI-20.
2. Any retreatment for stress incontinence including pelvic floor physical therapy; incontinence pessary; urethral bulking injection; repeat incontinence surgery
3. Surgical intervention for urinary retention (sling lysis or revision) at any time point post-operatively

Secondary outcome measures will assess the degree to which the study intervention influences adverse events intra- and post-operatively and will include the following:

1. Adverse events

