SAEs must be reported to the DSMB within two business days as outlined above in the DSMB section.

TABLE 1. Classification of Surgical Complications Clavien-DINDO Grade Definition for Sling attributed post-op events only

| | |
|-----------|---|
| Grade 1 | Any deviation from the normal postoperative course without the need for pharmacologic treatment. Allowed therapeutic interventions are: drugs as antiemetics, antipyretics, analgesics, physiotherapy |
| Grade II | Requiring pharmacological treatment with drugs other than such allowed for grade I complications Blood transfusions and total parenteral nutrition are also included |
| Grade III | Requiring surgical, endoscopic or radiological intervention |

| | |
|----------------------------|---|
| IIIA IIIB | Intervention not under general anesthesia Intervention under general anesthesia |
| Grade IV IVA IVB | Life-threatening complication (including CNS complications)* requiring IC/ICU management Single organ dysfunction (including dialysis) Multiorgan dysfunction |
| Grade V | Death |

Protocol Specific Reportable AEs include those determined to be related to the operative procedures or the device as listed below:

Bleeding
 Bladder Injury (Cystotomy or Bladder Trocar Perforation)
 Vaginal Wall Perforation
 Urethral Injury
 Bowel Injury
 Nerve Injury
 Intestinal Injury
 Infection (UTI, Vaginal, Pelvic Abscess)
 Bowel Obstruction
 Venous Thromboembolism
 Mesh Exposure
 Leg Pain or Difficulty Ambulating
 Fistula
 Urinary Retention
 Hematoma
 Bladder Outlet Obstruction
 Urgency “de novo”
 Stress or Urgency Incontinence (New or Worsening)
 Recurrent POP
 Other Urogynecologic Complications: _____

Please note that underlying diseases are not reportable as AEs unless there is an increase of severity or frequency during the course of the study. If an AE has not resolved at the time of AE Form completion, save form as incomplete in REDCap until resolved. Once resolved, update AE form, and enter into REDCap and save form as complete.

Adverse Event Definitions:

Adverse Event: any untoward medical occurrence, unintended disease or injury, or any untoward clinical signs (including abnormal laboratory finding) in subjects, whether or not related to the operative procedures

Serious Adverse Event: an adverse event that:

- Led to death
- Led to serious deterioration in the health of the subject that either resulted in
 - a life-threatening illness or injury

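### Bladder and urethral injury is searched for by cystoscopy in the retropubic technique only, so the between-arm comparison of this one Hypothesis 2 component leans towards the single-incision sling

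*Protocol*

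**What the plan says.** Under Standardized technique of RP sling placement, the protocol writes: "After placement of both trocars, cystoscopy with a 70-degree scope will be performed to assess for bladder and urethral injury". The purpose of the step is to find injury.

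Under Standardized technique of SIS placement, the sequence is a mid-urethral incision, then "The sling/needle assembly is advanced behind the ischiopubic rami in a transobturator trajectory toward the obturator space bilaterally", then tensioning, then "The adjustment thread is then cut short and the vaginal incision is closed with an absorbable suture", followed by the sham skin incisions. No inspection of the bladder or urethra is described. The section later adds: "Any intra-operative adverse events will be recorded on data collection forms". That covers recording, not how an injury would be found. Cystoscopy is mentioned nowhere else in the protocol.

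Hypothesis 2 expects fewer complications with SIS, "due to fewer sling related complications including urinary tract injury; bleeding; de novo or worsening urge incontinence symptoms". Specific Aim 2 is "To compare intra- and post-operative sling related complications, de novo or worsening urge incontinence symptoms and need for prolonged bladder drainage", RP versus SIS. Adverse events are the first secondary outcome, and the list of reportable events under Reporting Adverse Events names both bladder and urethral injury. Under Randomization and Masking, surgeons are acknowledged to be unmasked.

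**The concern.** A comparison of event counts is fair only if the events are looked for in the same way in both arms. Here one arm has a mandated search for a named outcome and the other has none. An injury that causes trouble later can be picked up in either arm. A small injury that would have stayed silent is reliably picked up only in RP.

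The imbalance points the way Hypothesis 2 predicts. If SIS shows fewer urinary tract injuries, the trial as written cannot say how much of the difference comes from the device and how much from not having looked. Any cystoscopy in an SIS patient is at the discretion of a surgeon who knows the arm.

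**Working it through.** **Side by side**

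| Item | RP | SIS |
|---|---|---|
| Check for bladder or urethral injury in the technique section | Cystoscopy after both trocars | None stated |
| Intra-operative adverse events recorded | Yes | Yes |
| Common method of detection | None stated | None stated |
| Surgeon knows the arm | Yes | Yes |

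**The plan's own figures.** The protocol gives no injury rate and no power figure for Hypothesis 2. Its only sample size is for the primary outcome, and it reproduces: (1.645 + 0.842)² × 2 × 0.82 × 0.18 / 0.12² = 126.7, so 127 per group. Then 254 × 1.10 = 279.4, or 280 in total and 140 per arm. The point does not depend on this; 140 is used below only to turn rates into counts.

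**Form of the bias.** Let p_R and p_S be the true injury proportions, and s_R and s_S the fractions detected. The observed difference, RP minus SIS, is p_R·s_R − p_S·s_S. With equal detection at s_R it would be s_R(p_R − p_S). The excess due to unequal looking is p_S(s_R − s_S). It is positive whenever SIS injuries are detected less completely than RP injuries, and it is proportional to the true SIS rate.

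**Illustration 1: equal true rates, s_R = 1 (assumptions, not protocol figures).**

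| True rate in both arms | Expected RP events | SIS events at s_S = 0.75 / 0.50 / 0.25 | Spurious difference (points) |
|---|---|---|---|
| 2% | 2.8 | 2.1 / 1.4 / 0.7 | 0.5 / 1.0 / 1.5 |
| 5% | 7.0 | 5.25 / 3.5 / 1.75 | 1.25 / 2.5 / 3.75 |
| 8% | 11.2 | 8.4 / 5.6 / 2.8 | 2 / 4 / 6 |

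**Illustration 2: SIS injury truly rarer.** Keep s_S = 0.50. If the true SIS rate is 2%, the bias is 0.02 × 0.50 = 1.0 point, or 1.4 events in 140. If it is 1%, the bias is 0.5 point, or 0.7 events. The RP rate does not enter when s_R = 1.

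**Chance of a false signal.** Under Illustration 1, I summed the binomial probabilities of all count pairs with fewer SIS events and a two-sided Fisher p below 0.05. With s_S between 0.50 and 0.25, the chance is 2% to 3% at a true rate of 2%, and 11% to 30% at 5%. A normal approximation gives higher values (10% and 20% at s_S = 0.50) but is rough with so few events. Typical tables are far from significance: Fisher p is 0.62 for 3 versus 1, 0.54 for 7 versus 4 and 0.17 for 7 versus 2.

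**The case against.** The strongest reply is that RP slings truly injure the bladder more often. The protocol's background says they carry the highest risk of such complications, that trans-obturator slings cause fewer perforations, and that SIS builds on the trans-obturator design. This stands as an argument about size: by the formula above, a rarer SIS injury leaves less to miss. It does not remove the problem, because the design still cannot separate a true difference from unequal detection.

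Second, cystoscopy is not prohibited in SIS, and some women may have it for their prolapse repair. That would narrow the gap. But the protocol does not govern the prolapse procedures and does not assure any such cystoscopy or its timing relative to sling passage.

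Third, the case report forms and the SIS training video are not available here, so the detection fields may already exist. That is possible; the protocol does not say so.

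Fourth, the reach is narrow. Urinary tract injury is one of seven items in Hypothesis 2 and is not separately listed as a secondary outcome. This is right.

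A reader might infer that half to three quarters of any observed reduction would be spurious. The documents do not support that: a 50% to 75% reduction only restates an assumed SIS detection of 50% to 25% with equal true rates, and the protocol's background argues against equal rates. Nor should anything be read into the Calendar of Events, which itemises no operative step, or into monitoring. The safety board's described inputs are graded post-operative sling events and progress reports, not a comparative table of intra-operative injuries.

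**Conclusion.** The point holds as an ascertainment weakness in one component of a secondary hypothesis. The text establishes that injury is searched for by mandate in RP only. The direction of the bias, towards SIS and towards Hypothesis 2, follows if SIS injuries are detected less completely as a result. The size is not established. Under the stated assumptions (140 per arm, full RP detection, half of SIS injuries detected) it is about 0.5 to 2.5 points for true SIS rates of 1% to 5%. It approaches zero if SIS injury is very rare or if most SIS patients have cystoscopy after sling passage.

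The bias concerns mainly injuries that would otherwise stay silent. The primary composite, made up of stress symptoms, retreatment and surgery for retention, does not include urinary tract injury, and the sample size is untouched. A reader might also take the two technique sections to contradict each other. They do not: they describe two different operations. The conflict is between that difference and an aim that compares the arms on what the one-sided step is there to detect.

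**What to change.** 1. Reconcile the two technique sections with Specific Aim 2 by stating how urinary tract injury is ascertained in each arm. Which operative procedure to use is for the investigators.
2. On the surgery form, in both arms, record whether cystoscopy was done, its timing relative to sling passage, and how each injury was detected. If the form already holds these fields, the protocol need only say so.
3. Report urinary tract injury by arm, first as all injuries and then split by mode of detection: at cystoscopy (mandated or discretionary), or recognised without cystoscopy or through later symptoms. Use the same classification in both arms.
4. State in advance that a difference resting on cystoscopy-only detections is not by itself evidence for Hypothesis 2.

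Simply dropping injuries found at mandated cystoscopy would not do. Only RP has the mandate, so SIS injuries seen at discretionary cystoscopy would still count while comparable RP injuries were set aside, and the bias could reverse.

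The cost is a few form fields, one added statement in the Aim 2 definition and a more cautious claim on this component. No additional procedure is required.
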